8.3 STATISTICAL ANALYSES

8.3.1 General Approach

The primary aims are to investigate how TMS alters the EEG biomarkers of successful memory performance and how memory state-related neural changes influence plasticity of the brain. Secondary aims for this protocol will include examining the MRI connectivity predictors of TMS effects.

8.3.2 Analysis of the Primary Endpoints

- Primary Endpoint 1: Investigate how TMS modulates EEG neural measures of successful memory and the relevance of modulation to behavioral performance
This aim will examine behavioral and EEG neural outcome measures (Primary Endpoints 1-4). We will perform 3x3 ANOVAs on each outcome measure with the factors trial type (successful/ unsuccessful/ spatial), stimulation site (parietal/ vertex/ none), and their interaction. We will particularly focus on the main effect of stimulation site to determine

the influence of parietal-TMS on memory performance and its neural correlates, and the interaction effect to determine the task specificity of TMS effects. Thresholds for significant effects will be set at $p<0.025$ following FDR correction for multiple comparisons.

- Primary Endpoint 2: Examine how memory task state influences susceptibility to plasticity via TMS and determine the optimal neural state for improving memory
This aim will examine behavioral and EEG neural outcome measures (Primary Endpoints 1-4). We will perform 3x3x2 ANOVAs on each outcome measure with the factors trial type (successful/ unsuccessful/ spatial), stimulation site (parietal/ vertex/ none), stimulation timing (pre-trial and mid-trial) and their interaction. We will particularly focus on the interaction effect of stimulation site and timing to determine the influence of memory task-state parietal-TMS on memory performance and its neural correlates, and the three-way interaction effect to determine the task specificity of state-dependent TMS effects. Thresholds for significant effects will be set at $p<0.025$ following FDR correction for multiple comparisons.

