3 OBJECTIVES AND ENDPOINTS

OBJECTIVES	ENDPOINTS	JUSTIFICATION FOR ENDPOINTS
Primary		
1. Investigate how TMS modulates EEG	1. Memory performance	1. Memory performance measures will allow us to

[figure not shown]
OBJECTIVES	ENDPOINTS	JUSTIFICATION FOR ENDPOINTS

neural measures of successful memory and the association of this modulation with behavioral performance
 
2. Examine how memory task state influences susceptibility to plasticity via TMS and determine the optimal neural state for improving memory
	
 • Accuracy: Percentage of successful (later remembered hit and correct rejection) vs unsuccessful (forgotten miss and false alarm) trials for item recognition (remember/familiar/new) and context recollection (spatial location) • d': Analysis of hits (correctly remembered as encoded) relative to false alarms (new objects labelled as encoded) for item recognition 
2. Late positive posterior ERP
 
 • ERP amplitude 500-700 ms after trial onset (encoding and retrieval) over parietal and occipital electrodes 
3. Theta/alpha power (secondary)
 
 • Power in the 4-13 Hz band 0-1000 ms after trial onset (encoding and retrieval) 
4. EEG functional connectivity (secondary)
 
 • Pearson correlation coefficients (r) between electrode time courses after trial onset (encoding and retrieval) 	
examine the effects of TMS on performance, as well as to sort successful vs unsuccessful trials for EEG analyses
 
2. The late positive posterior ERP has been previously shown to be a robust marker of successful memory performance²⁵
 
3. Task-induced changes in this frequency band have been previously associated with successful memory performance²⁶
 
4. fMRI functional connectivity modulation via network-targeted TMS has been previously associated with TMS-induced memory improvement. Whether EEG functional connectivity will be similarly altered, and the relevance to memory changes, remains unknown

Tertiary/Exploratory		
1. Search for MRI predictors of the	1. Baseline fMRI functional connectivity	It is hypothesized that TMS influences downstream targets

OBJECTIVES	ENDPOINTS	JUSTIFICATION FOR ENDPOINTS

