8 STATISTICAL CONSIDERATIONS

8.1 STATISTICAL HYPOTHESIS

The primary aims are to investigate how TMS alters the EEG biomarkers of successful memory performance and how memory state-related neural changes influence plasticity of the brain. Secondary aims for this protocol will include examining the MRI connectivity predictors of TMS effects.

- Primary Objective 1: Investigate how TMS modulates EEG neural measures of successful memory and the relevance of modulation to behavioral performance
 - Hypotheses
 - a. Network-targeted parietal-TMS will improve memory performance (context recollection; Primary Endpoint 1) relative to vertex-TMS trials
 - b. Relative to vertex-TMS, parietal-TMS will also increase the Late Positive Posterior ERP (Primary Endpoint 2) and theta power (Primary Endpoint 3) during encoding on successful trials, relative to unsuccessful trials
 - c. Parietal-TMS will alter EEG functional connectivity patterns (Primary Endpoint 4) at encoding during successful trials relative to unsuccessful trials
 - d. The EEG effects will correlate with memory improvement (Correlation, Primary Endpoint 1 and 2-4)
 - e. Parietal-TMS will not influence neural activity or accuracy for spatial trials, relative to vertex-TMS and no-TMS
- Primary Objective 2: Examine how memory task state influences susceptibility to plasticity via TMS and determine the optimal neural state for improving memory
 - Hypotheses
 - a. Network-targeted parietal-TMS during memory encoding will have a larger effect on memory performance (Primary Endpoint 1), relative to pre-trial parietal-TMS and vertex-TMS during encoding
 - b. Exploratory Analyses:
 - i. Parietal-TMS during memory encoding will increase the Late Positive Posterior ERP (Primary Endpoint 2) and theta-power (Primary Endpoint 3), relative to pre-trial parietal-TMS and vertex-TMS during encoding
 - ii. Additionally, parietal-TMS will alter EEG functional connectivity patterns (Primary Endpoint 4) during later-remembered trials, relative to pre-trial parietal-TMS and vertex-TMS during encoding
 - iii. Network-targeted TMS will not influence neural activity during arithmetic trials, relative to vertex-TMS and no-TMS

- *Exploratory Objective:* Determine MRI predictors of the effects of noninvasive stimulation

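### Section 8.3.2 makes success or failure of memory a factor in the model for memory performance itself, so the site and site × timing tests do not test context recollection and the trial-type interactions cannot show task specificity

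*Combined protocol and SAP*

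**What the plan says.** Section 8.3.2 states that it covers behavioural as well as EEG outcomes. For Objective 1 it sets one model for all of them: "We will perform 3x3 ANOVAs on each outcome measure with the factors trial type (successful/ unsuccessful/ spatial), stimulation site (parietal/ vertex/ none". An interaction term is included. One term gets the emphasis: "We will particularly focus on the main effect of stimulation site to determine". The section says what this term and the interaction are each meant to show: "the influence of parietal-TMS on memory performance and its neural correlates, and the interaction effect to determine the task specificity of TMS effects".

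For Objective 2 it adds timing (pre-trial or mid-trial): "We will particularly focus on the interaction effect of stimulation site and timing to determine the influence of memory task-state parietal-TMS on memory performance". The three-way interaction is read as the task specificity of state-dependent effects. The threshold is 0.025 after FDR correction.

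Section 3 defines the accuracy part of memory performance as "Percentage of successful (later remembered hit and correct rejection) vs unsuccessful (forgotten miss and false alarm) trials for item recognition" and for context recollection, and adds d' for item recognition. It says memory performance serves to examine TMS effects "as well as to sort successful vs unsuccessful trials for EEG analyses".

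In Section 8.1, hypothesis 1a reads "Network-targeted parietal-TMS will improve memory performance (context recollection; Primary Endpoint 1) relative to vertex-TMS trials" and hypothesis 1e reads "Parietal-TMS will not influence neural activity or accuracy for spatial trials, relative to vertex-TMS and no-TMS".

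Sections 8.1 and 8.3.4 use a plain parietal-minus-vertex difference, but only for exploratory correlations with MRI. No primary behavioural model without the success factor is given.

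**The concern.** For an ERP amplitude, splitting memory trials by later success is sensible: each class of trial has its own amplitude. For memory performance, the split is the outcome. A percentage correct cannot be broken down by correct and incorrect and then averaged over both without losing what it measures.

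Two readings are at stake. The site main effect and the site × timing interaction are meant to show whether parietal TMS changes memory. The interactions with trial type are meant to show that the change is specific to the memory task. If the factor is built from the outcome, neither term answers its question. A real memory gain could be reported as no TMS effect on memory, a spatial-task change as a memory effect, and a general gain as task-specific.

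**Working it through.** **Inputs from the documents.** Factor levels and roles of the tests: Section 8.3.2. Outcome definition: Section 3. Cell sizes: Table 1 in Section 4 (per task and experiment, 30 parietal, 30 vertex and 15 + 15 unstimulated trials). n = 32: Section 8.2.

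**The plan's own figure.** Section 8.2 derives 32 from η² = 0.44 and 0.28, α = 0.025 and power 0.80. Converting, f² = 0.44/0.56 = 0.79 and 0.28/0.72 = 0.39. A one-df within-subject test then needs 15-16 and at most 28 participants; at 32 its power is 0.99 and 0.86. The 32 is not reproduced, because the number of measurements, their correlation and any sphericity adjustment are not stated. Nothing below depends on it.

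**Step 1: shares that sum to 1.** Let s be the successful share at a site, 1 − s the unsuccessful share and q the spatial accuracy.
- Site mean = (s + (1 − s) + q)/3 = (1 + q)/3. Memory cancels.
- With site deviations a (memory) and b (spatial), the three cells deviate by a, −a and b. The site effect is b/3, so SS(site) = Σ3(b/3)² = Σb²/3.
- The residuals are a − b/3, −a − b/3 and 2b/3, so SS(trial type × site) = Σ(2a² + 2b²/3).
- The cancellation holds at each timing, hence also for site × timing.

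**Step 2: example.** Take s = 0.70/0.60/0.60 (parietal/vertex/none) and q = 0.90 throughout. Every site mean is 1.90/3 = 0.633. Memory rose by 10 points and the site effect is zero.

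**Step 3: specificity.** The interaction sum of squares is zero only if a and b are both zero, so it is a joint test of any effect in either task. For a 10-point parietal gain, Σa² = 0.0667² + 2 × 0.0333² = 0.00667, and Σb² is the same for a 10-point spatial gain.

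| Gain | Planned interaction SS | Two-level task × site SS, Σ(a − b)²/2 |
|---|---|---|
| Memory only | 0.0133 | 0.0033 |
| Equal in both tasks | 0.0178 | 0 |
| Spatial only | 0.0044 | 0.0033 |

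The planned interaction is largest when the effect is not specific.

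**Step 4: other ways to fill the cells.**
- Missed items count in neither context category. The two memory cells then sum to the hit rate h and the site mean is (h + q)/3. Hit rate is mixed with spatial accuracy, and context recollection drops out.
- Accuracy scored within success level: the cells are constants. d' has no value there, because it needs hits and misses, and false alarms and correct rejections, together.
- Trials sorted by item recall (stated in Section 4 for EEG only) with context as outcome: the context gain among hits enters with weight one-third, averaged with misses and spatial accuracy.

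**Step 5: illustrative rejection rates.** Assumed, not in the documents: memory success 50-70%, or hit rate 65-85% with context 55-75% among hits; spatial accuracy 80-93%; between-subject logit SD 0.5; subject-by-cell logit SD 0-0.2. n = 32, 30 trials per cell, α = 0.025, Greenhouse-Geisser correction, no FDR step. The last row assumes context accuracy of 65% for hits and 25% for misses.

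| Scenario | Planned site or site × timing | Planned trial-type interaction | Direct test |
|---|---|---|---|
| Sum to 1, memory +10 points | 2.0-2.2% | 94.9-99.8% | 94.7-99.8% (site, memory score) |
| Sum to 1, memory +5 points | 2.1-2.5% | 34.5-57.2% | 34.0-56.6% (site, memory score) |
| Sum to 1, +10 points mid-trial parietal only | 2.0-2.4% | 66.2-90.3% (three-way) | 65.8-90.0% (site × timing, memory score) |
| Sum to 1, both tasks +5 points | – | 47.9-77.3% | 1.9-2.8% (task × site) |
| Sum to 1, spatial only +3 points, base 80% to 93% | about 21-75% | – | – |
| Misses in neither category, context +10 points among hits | 2.0-2.5% | about 81-97% | 57.1-93.3% (parietal-vertex, all encoded) or 77.5-99.4% (recognised) |
| Sorted by item recall, context +10 points among hits | 19.5-41.3% | – | 84.4-97.0% (parietal-vertex, recognised) |

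Without a sphericity correction, which the plan does not mention, the planned trial type × site test rejects in about 4-5% of null runs at a nominal 2.5%, because s and 1 − s are perfectly dependent.

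**The case against.** The strongest reply is that the plan never says s and 1 − s will be entered. Section 3 ties sorting by success to the EEG analyses, Section 4 places the sorting rule under EEG, hypothesis 1a is a direct parietal-versus-vertex comparison, and d' cannot be computed within a success level. The sentence in 8.3.2 may be loose wording for an EEG model. The Memory Task text is also unclear: asking the quadrant of previously seen objects may refer to the object's true status, in which case missed items get a quadrant response too.

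This stands as far as intent goes: exact cancellation is conditional. It does not rescue the text. Section 8.3.2 names behavioural outcomes, assigns the terms to memory performance and offers no other primary model, and none of the fillings examined gives a clean test of hypothesis 1a.

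A second reply is that the ANOVA still finds the effect. That is right, both when the shares sum to 1 and when misses count in neither category. A successful-versus-spatial contrast within the interaction would even isolate memory minus spatial in the first case, but the plan names no such contrast.

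A third is that the rates rest on assumed values. They do; the spatial-only row moves from 21% to 75% with the base alone. Equal percentage points as the meaning of a non-specific effect is also a choice of scale, which matters near ceiling. The algebra needs none of these values.

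**Conclusion.** The point holds and should be fixed before analysis. As written, the Endpoint 1 model conditions on its own outcome. If the memory shares sum to 1, the two focal tests are exactly tests of spatial accuracy, where hypothesis 1e predicts no effect, and the trial-type interactions do not separate specific from general gains. If misses count in neither category, the site test mixes hit rate with spatial accuracy and does not test context recollection.

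A reader might infer that the trial cannot detect a TMS effect on memory, or that it will certainly be analysed with memory cancelled. The documents support neither: detection survives in the interactions with similar power, and the coding is unstated. Nor does this point show that 32 participants are too few. The harm is attribution to the wrong test and misread specificity. Leaving the coding open would also allow it to be settled after the data are seen.

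Confidence is high for the algebra and for the missing behavioural model. The rejection rates are illustrations on the assumptions listed. The three-level factor is sound for the EEG endpoints.

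**What to change.** In 8.3.2, for Endpoint 1 only:
- Drop successful/unsuccessful as a factor. Use context recollection as one score per stimulation cell, with one stated denominator (all encoded objects, or recognised objects) in every cell.
- Objective 1: site (parietal/vertex/none) on memory trials, key contrast parietal versus vertex.
- Objective 2: site × timing on that score, key contrast (parietal minus vertex, mid-trial) minus (parietal minus vertex, pre-trial).
- Task specificity: a separate two-level task (memory/spatial) × site test, and task × site × timing for Objective 2, with the accuracy scale stated.
- Item recognition and d': hit rate per cell with the session's common false-alarm rate, because lures are never encoded and have no stimulation status.
- State the sphericity correction for terms with more than one df.

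Keep the three-level factor for the EEG endpoints. Align the accuracy definition in Section 3, and the reference in 8.2 to the 8.3.2 ANOVAs, with the new models. The cost is wording in Sections 3, 8.2 and 8.3.2; no new data or participants are needed.

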4 STUDY DESIGN

This protocol is a single site study. The study will include a baseline 3T MRI session, and two experiments conducted during two sessions of simultaneous TMS, EEG, and cognitive testing (Figure 1). Both experiments will use the same participants to allow for within-subjects comparisons and the order of experiments will be counterbalanced. Participants who miss a session will be rescheduled or replaced (see Recruitment). Participants will make three visits to the lab, a baseline assessment session and two TMS/EEG sessions, for a time commitment of approximately 8 hours. TMS/EEG Session 1 will occur 1-31 days following the baseline visit and TMS/EEG Session 2 will occur 4-31 days following TMS/EEG Session 1 (Figure 1).

Figure 1. Study Design

[figure not shown]
On each TMS/EEG day, participants will undergo EEG recording using a 64-channel elastic cap. During recording, they will complete two blocks of a task, one for each experiment, which differ only in their timing of TMS delivery. Each block consists of 90 study trials of episodic memory encoding (45 trials) and spatial processing (45 trials) for a total of 180 trials (90 memory and 90 spatial processing) per TMS/EEG session (Table 1).

Table 1. Conditions and trial counts.

	Parietal Stimulation				Vertex Stimulation				TOTAL			
	Stim On		Stim Off		Stim On		Stim Off					
	Memory	Spatial	Memory	Spatial	Memory	Spatial	Memory	Spatial				
Experiment 1	30	30	15	15	30	30	15	15	180	360		
Experiment 2	30	30	15	15	30	30	15	15	180			

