TMS will be paired with task trials and consist of 2-second trains of continuous theta burst stimulation (cTBS; see Study Procedures). In Experiment 1, TMS will be delivered during the rest phase immediately prior to trial onsets (Figure 2). In Experiment 2, TMS pulses will occur during the trial while participants are actively engaged in the task (Figure 2). The order of experiments will be counterbalanced across subjects within each session. TMS will be delivered to an episodic memory network-connected location in posterior parietal cortex (see 4.4.2. TMS, below) or to the vertex as an inactive control condition, and the order of stimulation location will be counterbalanced across TMS/EEG sessions. One-third of trials will contain no stimulation as an additional control to examine behavioral and neural effects in the absence of the TMS sensory artifact (Table 1). Participants will then be tested on encoded items, also with EEG recording. EEG data will be examined in an event-related design, with timeseries following trial onsets compared across task (memory encoding, spatial processing, and memory retrieval) and stimulation (parietal-TMS, vertex-TMS, and no-TMS) conditions.

Figure 2. Experiment Design

Recruitment

Healthy participants will be recruited from the pool of individuals self-referring to the study directly and via the NIH Clinical Research Volunteer Program and via advertisements that will be pre-approved by the IRB. Although NIH employees will be allowed to participate, no direct solicitation of employees/staff by supervisors or co-workers will take place. Any recruitment material will be IRB approved. Participants who indicate interest will be pre-screened by phone. Pre-screening questions are listed in Appendix B. IRB-approved ads will be posted on NIH listservs with the permission of the moderator and IRB required statement on how the receiver was identified. Listservs may include NIH sponsored recruitment list serves such as (NIH HV recruitment list serv). Listserv announcement will include:

“You are receiving this message because your email address is included in the above NIH Listserv mailing list. The purpose of this message is to inform you of studies that are recruiting

Abbreviated Title: Task-dependent TMS and memory

Version Date: 11.15.22

volunteers at NIH, Bethesda, Maryland. The moderator of the listserv mailing list has permitted its use for this distribution”.

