Memory Task: This is a test of episodic memory, including item recognition and context recollection^{30,52,53}. In the task, participants will be shown a series of objects in one of four quadrants on the screen. They will be instructed to remember the objects and where they were located, both of which will be tested later. To ensure attention and for consistency with the spatial task (see below), they will be asked to indicate by button press whether the object is primarily used outdoors (e.g., a baseball) or indoors (e.g., a television). During the encoding phase, each object will be presented for 4 seconds with 4 seconds between trials. In Experiment 1, TMS will occur during a 2 second cue before each trial and in Experiment 2, TMS will occur in the first 2 seconds of stimulus object presentation. There will be 180 encoding trials, interspersed with 180 trials of the spatial task (described below). Trial order will be randomized. The retrieval phase will occur following the end of encoding. Participants will be shown, sequentially and in randomized order, the 180 encoded objects and 180 new lure objects, for a total of 360 trials. For all trials, they will respond with whether the object was old (previously seen) or new (not previously seen) and their confidence on a scale of 1-6 (1=confident new,

Abbreviated Title: Task-dependent TMS and memory

Version Date: 11.15.22

6=confident old) as a measure of item recognition. If the object was previously seen, participants will then be asked which quadrant the item was presented in to provide a measure of context recollection. We will use two different versions of the task with different and non-overlapping sets of objects at the two test sessions and the order of versions will be counterbalanced across participants.

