8.2 SAMPLE SIZE DETERMINATION

All experiments in this protocol are powered based on the primary outcome, which relates to the effects of TMS on memory and its neural correlates.

A power analysis was conducted using G*Power v3.1.9.7. We used a repeated-measures, within-factors ANOVA based on a previous study with a similar design³⁹. Like the proposed experiments, this study delivered 2-second trains of TMS prior to trials of memory encoding or a control task and examined the effects on later memory performance and on neural activity, in this case hippocampal fMRI activity, during encoding. They used a three-way repeated-measures ANOVA to examine the interactions between TMS presence (on vs off), frequency (theta-burst vs 12.5 Hz beta), and location (parietal cortex vs supplementary motor area) and found an effect size of theta burst parietal-TMS on memory performance of $\eta^2=0.44$ and fMRI hippocampal activity of $\eta^2=0.28$. As the proposed analyses will also use three-way repeated-measures ANOVAs (see Section 8.3.2), we calculated subject number based on these effect sizes, power of 0.80, and $\alpha = 0.05$ shared across two primary outcomes, memory performance and the late positive posterior ERP ($\alpha = 0.025$ for each outcome). Thirty-two participants with complete data will be needed. To achieve $n=32$, we will recruit up to 50 subjects to account for potential non-completion (e.g., screen failure, subject withdrawal) or unusable data (e.g., due to noise).

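### Section 8.3.2 compares parietal with vertex stimulation across two sessions but has no session, order or object-set term; if a common shift exists, the site test is conservative, and modelling it costs about 2 df

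*Combined protocol and SAP*

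**What the plan says.** Section 8.3.2 specifies for Objective 1 "3x3 ANOVAs on each outcome measure with the factors trial type (successful/ unsuccessful/ spatial), stimulation site (parietal/ vertex/ none), and their interaction", and adds: "We will particularly focus on the main effect of stimulation site". The Objective 2 model adds stimulation timing. Neither model contains session, site order or task version.

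Section 4 fixes the layout of the comparison:
- Site: "the order of stimulation location will be counterbalanced across TMS/EEG sessions", so each session uses one site.
- Interval: "TMS/EEG Session 2 will occur 4-31 days following TMS/EEG Session 1". The Schedule of Activities implies a different window (nominally Day 4 to Day 13), but on either reading the sessions are on separate days.
- Memory task: "two different versions of the task with different and non-overlapping sets of objects at the two test sessions", with version order counterbalanced across participants. The spatial task also has two versions; counterbalancing of these is not stated.
- Within a session: "they will complete two blocks of a task, one for each experiment, which differ only in their timing of TMS delivery". Both timings are therefore run at each session.
- No-stimulation condition: "One-third of trials will contain no stimulation as an additional control". These trials occur in both sessions.

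Section 8.2 bases the sample size on "a repeated-measures, within-factors ANOVA based on a previous study with a similar design", with η² = 0.44 for memory and 0.28 for hippocampal fMRI activity, power 0.80, alpha 0.025 for each of two primary outcomes, and 32 complete participants.

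**The concern.** This is a two-period crossover for parietal against vertex, analysed without a period term. Suppose scores at the second session differ from the first by a common amount (practice, familiarity with stimulation), or one object set is easier. That amount then enters the parietal-minus-vertex difference with a plus sign in one order and a minus sign in the other. With equal orders it averages out of the estimate, but it stays in the spread of the differences, which is the error term for the site test. The interval is wider than it need be, and the test rejects less often than its nominal level. The trial already bears the effort of counterbalancing, and the analysis leaves the return unused.

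Exposure is limited to two places. One is the ERP site main effect that 8.3.2 singles out. The other is any plain parietal-minus-vertex contrast, such as context recollection (section 8.1, Objective 1, hypothesis a).

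**Working it through.** **Inputs.** From section 8.2: n = 32, alpha = 0.025, η² = 0.28 and 0.44. Assumed, because the documents do not give it: a common shift s, in SDs of the within-person parietal-vertex difference, with 16 participants per order.

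**The plan's own figure.** Section 8.2 does not state the number of measurements, their correlation or the noncentrality convention, so 32 cannot be uniquely reproduced. With f² = η²/(1 − η²) and λ = N × f², three levels, alpha 0.025 and power 0.80, N = 32 results. This was the only one of 35 combinations of convention and number of levels at those inputs to give 32; the combinations ranged from 3 to 60. The match does not show what was done, so λ = 32 × f² is a working assumption.

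**Set-up.** For each participant, D = τ ± s + error, where the error has SD 1.
- η² = 0.28: f² = 0.28/0.72 = 0.389, λ = 32 × 0.389 = 12.4.
- η² = 0.44: f² = 0.44/0.56 = 0.786, λ = 32 × 0.786 = 25.1.
- Unmodelled: the mean of D is unbiased, and its estimated variance has expectation 1 + 32s²/31. Test on F(1, 31).
- Modelled (site order, and object set paired with parietal, each by site): variance back to 1. Test on F(1, 29).

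At s = 0.5 the unmodelled variance is 1 + 32 × 0.25/31 = 1.258, so the standard error is √1.258 = 1.12 times as large. The critical t moves only from 2.356 to 2.364 when the terms are added, so the interval narrows by 1 − (2.364/2.356)/1.1216, just over 10%.

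**Results.**

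| Shift s (SD) | 0 | 0.25 | 0.5 | 0.75 | 1.0 | Modelled |
|---|---|---|---|---|---|---|
| 1-df contrast, η² = 0.28 | 0.87 | 0.86 | 0.81 | 0.71 | 0.57 | 0.87 |
| Three-level site test, η² = 0.28 | 0.81 | 0.80 | 0.76 | 0.69 | 0.59 | 0.81 |

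The three-level row also assumes that the no-stimulation mean lies midway between the other two and is averaged over sessions. It applies to the site main effect of the 3x3 model: in simulated 32 × 3 × 3 data the site F equals the one-way F on trial-type averages (both 1.511326 on 2 and 62 df).

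- Type I error of the unmodelled 1-df contrast, nominal 0.025: 0.021, 0.013 and 0.002 at 0.25, 0.5 and 1.0 SD.
- Memory at η² = 0.44, 1-df contrast: 0.988 at 0.5 SD and 0.975 at 0.75 SD, against 0.995 modelled.
- No shift: adding both terms moves power from 0.873 to 0.871 (1-df) and from 0.809 to 0.807 (three-level, error df 62 to 58). Break-even is near s = 0.08.

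**Where the shift cancels.** Hypothesis b under Objective 1 in section 8.1 compares successful with unsuccessful trials, so a shift common to trial types drops out. Site × timing, the focus for Objective 2, contrasts two blocks within the same session, so a shift common to both timings drops out.

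**Memory cells.** Section 3 defines accuracy as the percentage of successful against unsuccessful trials. If those two percentages are used as cells, they sum to 100 at every site. Memory then contributes nothing to the site main effect, with or without a session term.

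**Hypothesis d (correlation of EEG effects with memory improvement).** Its scores are not defined. With no true association and a 5% test, plain parietal-minus-vertex differences on both measures give false positives of 6% and 20% at shifts of 0.25 and 0.5 SD. If the EEG score is successful minus unsuccessful, or if site order is partialled out, the rate stays at 5%.

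**The case against.** Relying on counterbalancing without modelling order is a defensible choice. The estimate is unbiased when orders are balanced, and the error is on the conservative side. The size of the gain rests on a shift that the documents do not give. At 0.25 SD it is about 0.01 in power, and at 0.5 SD the 1-df contrast still meets the planned 0.80. The planning η² comes from an earlier repeated-measures study whose error may already contain session variation. If so, n = 32 is not short: the contrast has 0.88 and 0.89 unmodelled against 0.89 and 0.94 modelled at 0.25 and 0.5 SD. All of this stands, and it limits the point to an improvement.

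It also stands that the terms are not free. They cost 2 df and lose slightly if there is no shift. The version term is estimable only if site order and version order are crossed, and section 4 says only that each is counterbalanced.

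A reader might go further and infer that the site effect is confounded with session, that the trial is underpowered, or that hypothesis b and Objective 2 are compromised. The documents do not support these readings. Site order is counterbalanced, no shift size is given, and a common shift cancels in those contrasts. Nor does the 20% figure for hypothesis d describe the plan: it needs plain-difference scoring, which is not specified, and a 0.5 SD shift in both measures.

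The objection does not give a reason to leave the terms out. The cost is known and trivial, and adding them after the results are seen would look data-driven.

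**Conclusion.** The point holds as a cheap improvement in precision and prespecification. The parietal-vertex comparison is made between sessions, and the model in 8.3.2 does not use the counterbalanced factors. If a common shift exists, the ERP site main effect and plain parietal-minus-vertex contrasts are tested conservatively. At η² = 0.28, 1-df power falls from 0.87 to 0.81 at 0.5 SD and to 0.57 at 1.0 SD, against 0.87 modelled. Memory at η² = 0.44 has power to spare.

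These figures rest on the assumed shift, on λ = 32 × f², and on 16 completers per order. If completers split unevenly, part of the shift stays in the estimate: at 18:14, (18 − 14)/32 = one-eighth of it. A fixed session term removes only the average shift and leaves participant-by-session variation in the error.

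**What to change.** In 8.3.2, keep the planned ANOVA and add site order as a between-participant factor with its interaction with site. The interaction does the work; a main effect alone leaves the within-participant error unchanged.

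State whether site order and version order are crossed.
- If they are, also add the object set paired with parietal stimulation, with its interaction with site. Version order (the set used first) is not a substitute, because the object-set shift then sits in site order × version order × site.
- If the two orders are locked together, version is aliased with site and cannot be modelled.
- State the version order for the spatial task as well.

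An equivalent is a session-level mixed model with session and version as fixed effects, no-stimulation results kept by session, and random intercepts for participant and participant-by-session. Test the parietal-vertex contrast against its own error. With a participant intercept only, simulated type I error was 3.0% to 5.4% at a nominal 2.5%, against 2.3% to 2.8% with the contrast's own error.

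For memory, apply the terms to the accuracy or d' contrast, not to percentages successful and unsuccessful used as cells. Define the scores for hypothesis d. If both are plain parietal-minus-vertex differences, partial out site order; otherwise this is not needed.

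The cost is a few lines of text and no new data: 2 error df in the 1-df contrast and about 0.002 power if there is no shift.
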